8.2.2. Exploratory secondary efficacy endpoints and analyses

All endpoints in this section are exploratory. No sensitivity analyses and adjustment for multiple comparisons will be conducted. Nominal p-values will be used to examine any trends in these endpoints.

8.2.2.1. Change in HbA_{1c} from baseline to week 24 in randomized subjects who have been prescribed sulfonylurea to control their diabetes

Same MMRM ANCOVA model as in section 8.1.1 will be used for this analysis. Analysis will be conducted based on ITT and PP analysis set. Same sensitivity analysis as in section 8.1.2 will be repeated. Subgroup analysis will be conducted by baseline HbA_{1c} category and baseline eGFR categories.

8.2.2.2. Changes from baseline in HbA_{1c} and FPG over time

Of interest is the difference between treatments on these two endpoints across all post-baseline time points with sufficient number of values. If for any treatment arm, less than 20 subjects completed the assessment in the analysis visit window, the visit will not be included in the analysis. Both endpoints will be analyzed using MMRM model with the change from baseline values across all post-baseline visits used as dependent variable. The fixed effect will include baseline eGFR (≥ 60 or < 60 mL min⁻¹ [1.73m]⁻²), baseline BMI ($<$ or ≥ 25 kg m⁻²), and history of heart failure (yes or no), insulin use or not, treatment, visit, treatment and visit interaction, other hypoglycemic agent use (no change, after relaxation, or after intensification), treatment and other hypoglycemic agent use interaction, and baseline value. For each endpoint, treatment difference in least squares means will be estimated by visit from the model with the corresponding p-values and the two-sided 95% CIs of the difference between treatments.

Analysis of HbA_{1c} over time will also be conducted for subjects who have been prescribed insulin or sulfonylurea to control their diabetes.

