9.6.2 Exploratory Efficacy Endpoints

The exploratory secondary efficacy endpoints include:

- Change from baseline in HbA1c over time
- Change from baseline in FPG over time
- Change from baseline in body weight over time
- Change from baseline in SBP over time
- Requirement of additional anti-diabetic medications, including insulin; and time to first use of additional anti-diabetic medication
- Requirement of reduced anti-diabetic medications, including insulin dose over time
- Hospitalization for heart failure in all subjects and in subjects with a history of heart failure
- time to hospitalization for heart failure in subjects in all subjects and in subjects with a history of heart failure

For changes from baseline in HbA1c, FPG, body weight, and SBP over time, a similar MMRM ANCOVA model will be used as for the key secondary efficacy endpoints. Of interest in the MMRM ANCOVA model is the difference between treatments on these endpoints across all post-baseline time points. Also, changes from baseline for each endpoint will be estimated and analyzed at each study visit using this MMRM model. Specifically, for each endpoint, treatment difference in least squares means will be estimated by visit from the model with the corresponding p-values and the two-sided 95% CIs of the difference between treatments.

Endpoints measuring proportions over time will be analyzed using generalized estimating equation (GEE) logistic regression using similar independent variables as the MMRM ANCOVA models above (the treatment-by-visit interaction term will be removed if not significant), and using an unstructured correlation structure (or autoregressive(1) if the model with the unstructured structure does not converge). Of interest is the difference between treatments across all post-baseline time points. Also, odds ratios will be estimated from the model with the corresponding p-values and their two-sided 95% CIs presented at each visit. For time-to-event endpoints, Cox proportional hazards models with treatment and randomization stratification factors as the covariates will be used to estimate the hazard ratio of the endpoint, p-value and its two-sided 95% confidence interval comparing bexagliflozin to placebo. Subjects who withdraw from the trial and for whom no follow up event data are collected (i.e., lost to follow-up subjects) will be censored at the last known follow-up.

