- b. After the non-monotone missing data have been imputed, the remaining monotone missing data will be imputed within each treatment arm and subgroup, defined by whether subject completed 24 week of study treatment, using regression approach. The predictors for the regression imputation model at any time point will be HbA_{1c} at all previous time points, including baseline. Imputations will be performed using a sequence of regression-based imputations (using PROC MI statement MONOTONE REG) at each post-baseline time point.
- c. Imputed data in each of the multiple imputed datasets will be analyzed using a mixed model repeated measures (MMRM) approach. The MMRM model will include treatment, visit, treatment-by-visit interaction, region, visit, treatment, treatment-by-visit interaction, baseline eGFR categories (<60 or ≥60 mL min⁻¹ per 1.73 m²), baseline BMI (< or ≥25 kg m⁻²), and history of heart failure (yes or no), insulin use or not, as fixed effects and the corresponding baseline HbA_{1c} as a fixed effect covariate. The analysis will evaluate the mean change from baseline in HbA_{1c} over the 24 week double blind treatment period. An unstructured covariance will be used to model the within subject correlation. The Kenward Roger approximation will be used to estimate denominator degrees of freedom. If the model with the unstructured covariance structure does not converge, an autoregressive(1) covariance structure will be used. HbA_{1c} values obtained after the start of intensification of hypoglycemic agent will not be excluded from the analysis. The treatment and treatment by visit interaction terms allow for comparisons of the treatment groups at each visit, and over week 6 to week 24. Least squares (LS) mean treatment differences between the bexagliflozin group and the placebo group at week 24 will be estimated from the model. The LS mean results from all imputed datasets will be combined using the Rubin's combination rule (PROC MIANALYZE).

If no sufficient week 24 values from treatment discontinued subjects are available for imputation, MMRM analysis will be performed using all available data. Method described in above step c will be utilized.

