Descriptive statistics (n, mean, Q1, median, Q3, SD, minimum, and maximum) will be reported by treatment arm and all observed visits. The least squares means, differences between LS means, a 2-sided 95% confidence interval for each difference, and p-values from the model effects up to week 24 visit will be presented. In addition, the observed change from baseline for all available visits with standard errors, LS means with

standard errors of the change from baseline over time and difference between treatment arms with 95% will be presented graphically for the ITT population.

For supportive analyses, the primary efficacy endpoint will be analyzed with observed available data using the PP analysis set in a similar manner as above.

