8.1.2. Sensitivity Analyses

Randomized subjects who withdraw consent to participate in the study will not be replaced. The early termination rate is estimated to be 6.5% annually. To the extent possible, attempts will be made to minimize the amount of missing data through measures planned in the study conduct, but if data are missing for the primary endpoints and the first key secondary endpoint (change in HbA_{1c} for subjects who have been prescribed insulin), the number, timing, pattern, and reason for the missing value will be summarized. The reason for missing values will be evaluated to investigate possible implications of missing values for efficacy assessments. The dropout patterns will be assessed by Kaplan-Meier plots, if applicable, to assess whether they differ between treatment arms. If there are missing values for the primary and key secondary analysis, all observed data will be analyzed and data obtained after rescue will not be excluded.

To evaluate the impact from missing data and intensification of hypoglycemic agent, the following sensitivity analyses will be conducted:

- 1) Tipping point analysis will be conducted. Data after intensification of hypoglycemic agent will be considered as missing. Following steps will be followed:
 - a. Create monotone missing data as step a in section 8.1.1;
 - b. Regression approach under MAR will be used to generate complete datasets. The predictors for the regression imputation model at any time point will be region, baseline eGFR categories (<60 or ≥ 60 mL min⁻¹per 1.73 m²), baseline BMI category (< 25 kg m⁻² or ≥ 25 kg m⁻²), history of heart failure (yes or no), insulin use or not, and HbA_{1c} at all previous time points, including baseline. The first imputed values will be penalized or rewarded based on the treatment subject received:
 - Subjects in the bexagliflozin group: missing value will be analyzed assuming the treatment effect is worsened by $\delta 1$ (where $\delta = 0.1$ to 0.5, in step of 0.1) compared to the subjects who have no missing value in the reduction of HbA_{1c} value;

- Subjects in the placebo group: missing value will be analyzed assuming the treatment effect is better by δ_2 (where $\delta = 0$ to 0.5, in step of 0.1) compared to the subjects who have no missing value in the reduction of HbA_{1c} value;

The penalty or reward will not be applied to the values from later time points as these values are penalized or rewarded through regression on previous time points.

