8.2.2.3. Changes from baseline in SBP and weight over time

Both endpoints will be analyzed using MMRM model with the change from baseline values across all post-baseline visits used as dependent variable. The fixed effect will include baseline eGFR (≥ 60 or < 60 mL min⁻¹ [1.73m]⁻²), baseline BMI ($<$ or ≥ 25 kg m⁻²), and history of heart failure (yes or no), insulin use or not, treatment, visit, treatment and visit interaction, and baseline value. For each endpoint, treatment difference in least squares means will be estimated by visit from the model with the corresponding p-values and the two-sided 95% CIs of the difference between treatments.

8.2.2.4. Proportions of subjects with intensification and relaxation of hypoglycemic agent (i.e. requirement of additional anti-diabetic medications and with requirement of reduced anti-diabetic medications)

These endpoints will be analyzed using logistic regression. The model will include terms for treatment, region, baseline eGFR categories (<60 or ≥ 60 mL min⁻¹ per 1.73 m²), baseline BMI ($<$ or ≥ 25 kg m⁻²), and history of heart failure (yes or no), insulin use or not,

and baseline HbA_{1c}. The LS mean proportions and the two-sided 95% CI for each treatment will be presented. Also, odds ratio of treatment difference of bexagliflozin group over the placebo group will be estimated from the model with the corresponding p-values and their two-sided 95% CIs presented. Analysis will also be conducted for subjects who have been prescribed insulin or sulfonylurea to control their diabetes.

8.2.2.5. Proportions of subjects with hospitalization of heart failure in all subjects, with hospitalization of heart failure in subjects with a history of heart failure

These endpoints will be analyzed using logistic regression. The model will include terms for treatment, region, baseline eGFR categories (<60 or ≥60 mL min⁻¹ per 1.73 m²), baseline BMI (< or ≥25 kg m⁻²), history of heart failure (yes or no), insulin use or not, and baseline HbA_{1c}. Odds ratios will be estimated from the model with the corresponding p-values and their two-sided 95% CIs. The odds ratios of bexagliflozin group over the placebo group will be estimated from LS means based on the model with the corresponding p-values and their two-sided 95 % CIs presented.

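### SAP 8.2.2.2 adjusts the exploratory HbA1c and FPG over-time differences for post-randomization therapy changes, so they are not the randomized effect and depend on LS-mean weights the SAP does not state

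*Combined protocol and SAP*

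**What the plan says.** SAP 8.2.2.2 models change from baseline in HbA1c and FPG by MMRM. Besides baseline covariates, treatment, visit and treatment-by-visit, the fixed effects are "other hypoglycemic agent use (no change, after relaxation, or after intensification), treatment and other hypoglycemic agent use interaction, and baseline value". LS-mean treatment differences, p-values and 95% CIs are reported at each visit. There is no visit-by-status term, and nothing says how LS means are weighted over the three status levels. SAP 6.2.7 and 6.2.8 define intensification and relaxation as changes during treatment.

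Other parts of the plan handle these changes differently:

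- **Protocol 9.6.2**, for the same endpoints: "a similar MMRM ANCOVA model will be used as for the key secondary efficacy endpoints". The key secondary model in protocol 9.6.1 has no post-randomization covariate.
- **SAP 8.2.2.3** (SBP and weight over time) ends its list of terms with "insulin use or not, treatment, visit, treatment and visit interaction, and baseline value"; there is no status term.
- **SAP 8.1.1** (primary analysis): HbA1c values "obtained after the start of intensification of hypoglycemic agent will not be excluded from the analysis". The model evaluates change "over the 24 week double blind treatment period", and "p-values from the model effects up to week 24 visit will be presented".
- **SAP 8.1.2** (tipping point): "Data after intensification of hypoglycemic agent will be considered as missing".

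SAP 8.2.2 calls its endpoints exploratory, with nominal p-values and no sensitivity analyses. The SAP revision log records the added covariate at version 1.4. SAP section 12, which lists changes from the protocol, does not mention it.

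**The concern.** Status is a consequence of the treatment period. Under protocol 5.2.5, therapy changes are guided by self-monitored glucose thresholds up to week 24, and afterwards by SMBG, FPG and HbA1c. Two of those three are the outcomes being modelled. SAP 8.2.2.4 and 8.2.2.6 compare the arms on intensification and relaxation as endpoints. A difference adjusted for such a variable is not the difference randomization supports, yet 8.2.2.2 says its interest is simply the difference between treatments over time.

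The adjusted result is not cleanly an effect at constant background therapy either. Read literally, SAP 6.2.7 and 6.2.8 count only the first change: an intensification that follows a relaxation is not one, and a decrease that follows an intensification is not a relaxation. The relaxed level could then hold subjects who were later re-intensified.

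What is at stake is interpretation, not error control. For FPG at all visits and HbA1c after week 24, this is the only clearly planned source of model-based p-values. SAP 8.1.1 also plans an HbA1c figure over time ("difference between treatment arms with 95% will be presented graphically for the ITT population") but does not say whether the model-based part runs past week 24. For HbA1c at weeks 6 to 24, the report will hold two sets of by-visit differences that treat intensification differently, without explanation.

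**Working it through.** There is no stated figure to reproduce; the point concerns model specification.

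**Step 1: algebra.** Let d_v be the treatment difference at visit v in the no-change level, g_rel and g_int the treatment-by-status coefficients, and w_rel and w_int the LS-mean weights. Then

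reported difference at visit v = d_v + w_rel × g_rel + w_int × g_int.

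With equal weights, w_rel = w_int = 1/3. With observed margins, each weight is the share of records at that level. With no visit-by-status term, the same added amount applies at every visit, including week 6. The two weightings differ by

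g_int × (1/3 − p_int) + g_rel × (1/3 − p_rel),

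where p is the record share. With p_int = 0.074 and g_rel = 0:

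- g_int = 0.5 gives (0.333 − 0.074) × 0.5 = 0.13.
- g_int = 0.1 gives (0.333 − 0.074) × 0.1 = 0.03.
- If both interactions are zero, the weights do not matter.

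**Step 2: illustrative simulation.** From the documents: 1100 vs 550 subjects and SD 1.1 (protocol 9.2), and effects of 0.22 (protocol 9.2) and 0.79 (protocol 3.3.2) for one variant. Everything else is assumed:

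- seven visits (weeks 6, 12, 24, 36, 48, 72, 96), complete data, within-subject correlation 0.7;
- drug effect −0.50;
- status fixed at the first change, none before week 6, driven by the previous HbA1c, with no unmeasured common cause of status and HbA1c;
- middle rates: 11.5% (bexagliflozin) vs 18.1% (placebo) intensified by the last visit; 7.4% of records after intensification and 7.6% after relaxation.

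Both models used an unstructured covariance.

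| Assumed effect of therapy change | Visit | Without status terms | With, equal weights | With, observed margins |
|---|---|---|---|---|
| (a) None | any | −0.50 | −0.50 | −0.50 |
| (b) Same in both arms: intensification −0.7, relaxation +0.3 | week 24 | −0.47 | −0.50 | −0.50 |
| (b) | last | −0.44 | −0.50 | −0.50 |
| (c) Intensification −0.5 bexagliflozin, −1.0 placebo | week 6 | −0.50 | −0.33 | −0.46 |
| (c) | week 24 | −0.44 | −0.33 | −0.46 |
| (d) Intensification −0.9 bexagliflozin, −0.6 placebo | last | −0.48 | −0.60 | −0.52 |

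Hand check with the Step 1 formula:

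- (c) g_int = −0.5 − (−1.0) = 0.50: −0.50 + 0.50/3 = −0.33; −0.50 + 0.074 × 0.50 = −0.46.
- (d) g_int = −0.9 − (−0.6) = −0.30: −0.50 − 0.30/3 = −0.60; −0.50 − 0.074 × 0.30 = −0.52.

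Scenario (b) with a true effect of −0.22 gave −0.19 without and −0.22 with the status terms at the last visit; with −0.79 it gave −0.69 and −0.79. With 3.2% to 17.2% of records after intensification, departures ran from 0 to about 0.18 points, in either direction. Monte Carlo error was at most 0.004. The SE was 1.1 to 1.5 times the unadjusted SE with equal weights and 1.0 to 1.1 times with observed margins.

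**Step 3: second simulation, different assumed rates.** Where the drug had an effect, the adjusted difference exceeded the randomized one in magnitude by 0.03 to 0.15 points at week 96. With the drug effect reduced by 0.2 after either change, week 24 was −0.48 without status, −0.37 with equal weights and −0.49 with observed weights. Sampling SDs at 1650 subjects were 0.048, 0.062 and 0.049.

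**The case against.** The term was added deliberately and the revision log says so. The protocol promised only a similar model. SBP and weight are imperfect comparators, since glucose-lowering drugs act most directly on HbA1c and FPG. That shows intent, but not what the adjusted difference estimates or how it is weighted.

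The stakes are low, and descriptive comparisons without status are planned: SAP section 8 summarizes all continuous efficacy data by arm and visit, and 8.1.1 gives model-based HbA1c differences to week 24. Both points stand. What is missing is narrower: a model-based CI and p-value without status for FPG and for later HbA1c.

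The magnitude rests on assumption. The largest shifts need a sizeable interaction that nothing in the documents supports. In (b), week 24 moves by 0.03, against an SE of about 1.1 × √(1/1100 + 1/550) = 0.057. This stands. So does the criticism of the week 6 row: protocol 3.2.2 and 5.2.5 give an intensification threshold for weeks 1 to 6, so earlier changes are allowed and a simulation with none is an extreme case.

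Finally, an effect net of unequal rescue is a legitimate question, and in (b) the adjusted model recovers the assumed −0.50. But that simulation has no unmeasured confounding, so it cannot validate the adjustment. The first-change-only reading is also an interpretation, because 8.2.2.2 does not say how status is coded after a reversal.

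**Conclusion.** The concern holds. The over-time HbA1c and FPG differences condition on a variable set after randomization, driven by glucose and compared between arms as an outcome. They are therefore not the randomized difference that keeps post-intensification values. With the treatment interaction and no visit-by-status term, they also depend on unstated weights. These conclusions follow from the model as written and need no simulation.

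The size is unknown. The range of 0 to about 0.18 HbA1c points comes from assumed rates and effects and should not be read as expected bias. It is zero if therapy changes have no effect. The weights matter only if the interaction is not zero. The primary test and the key secondary hierarchy are untouched. The change is worth making because the affected results otherwise have no clearly planned model-based counterpart.

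**What to change.** Take the main over-time differences, p-values and CIs for HbA1c and FPG from the 8.2.2.2 model without the status term and its treatment interaction. Suggested text:

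> Fixed effects: baseline eGFR category, baseline BMI category, history of heart failure, insulin use, treatment, visit, treatment-by-visit interaction and baseline value. All observed values are used, including those after intensification or relaxation.

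This has the form of SAP 8.2.2.3 and handles intensification as the primary analysis does. It does not reproduce the protocol's stratification-factor covariates, or the primary model's region term and retrieved-dropout imputation, so the two sets of HbA1c differences to week 24 will still not be identical. It only removes the conditioning on status.

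If the status-adjusted model is kept, label it supplementary, state what it estimates and its LS-mean weights (for example, observed margins), and list it in SAP section 12.

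The cost is SAP wording only, with no new data, and one extra model per endpoint if both are kept.

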8.2.2.3. Changes from baseline in SBP and weight over time

Both endpoints will be analyzed using MMRM model with the change from baseline values across all post-baseline visits used as dependent variable. The fixed effect will include baseline eGFR (≥ 60 or < 60 mL min⁻¹ [1.73m]⁻²), baseline BMI ($<$ or ≥ 25 kg m⁻²), and history of heart failure (yes or no), insulin use or not, treatment, visit, treatment and visit interaction, and baseline value. For each endpoint, treatment difference in least squares means will be estimated by visit from the model with the corresponding p-values and the two-sided 95% CIs of the difference between treatments.

8.2.2.4. Proportions of subjects with intensification and relaxation of hypoglycemic agent (i.e. requirement of additional anti-diabetic medications and with requirement of reduced anti-diabetic medications)

These endpoints will be analyzed using logistic regression. The model will include terms for treatment, region, baseline eGFR categories (<60 or ≥ 60 mL min⁻¹ per 1.73 m²), baseline BMI ($<$ or ≥ 25 kg m⁻²), and history of heart failure (yes or no), insulin use or not,

and baseline HbA_{1c}. The LS mean proportions and the two-sided 95% CI for each treatment will be presented. Also, odds ratio of treatment difference of bexagliflozin group over the placebo group will be estimated from the model with the corresponding p-values and their two-sided 95% CIs presented. Analysis will also be conducted for subjects who have been prescribed insulin or sulfonylurea to control their diabetes.

8.2.2.5. Proportions of subjects with hospitalization of heart failure in all subjects, with hospitalization of heart failure in subjects with a history of heart failure

These endpoints will be analyzed using logistic regression. The model will include terms for treatment, region, baseline eGFR categories (<60 or ≥60 mL min⁻¹ per 1.73 m²), baseline BMI (< or ≥25 kg m⁻²), history of heart failure (yes or no), insulin use or not, and baseline HbA_{1c}. Odds ratios will be estimated from the model with the corresponding p-values and their two-sided 95% CIs. The odds ratios of bexagliflozin group over the placebo group will be estimated from LS means based on the model with the corresponding p-values and their two-sided 95 % CIs presented.

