2.2 Secondary Efficacy Objectives

The key secondary efficacy objectives are:

- To evaluate the effect of bexagliflozin compared to placebo on the change in HbA1c from baseline to week 24 in randomized subjects who have been prescribed insulin to control their diabetes
- To evaluate the effect of bexagliflozin on the change in body weight from baseline to week 48 in randomized subjects with a BMI ≥ 25 kg/m² compared to placebo
- To evaluate the effect of bexagliflozin on the change in systolic blood pressure (SBP) from baseline to week 24 in subjects with baseline systolic blood pressure ≥ 140 mmHg compared to placebo

Additional exploratory efficacy objectives are:

- To assess the effect of bexagliflozin treatment on the change in HbA1c versus placebo over time
- To evaluate the effect of bexagliflozin treatment on the change in fasting plasma glucose (FPG) versus placebo over time
- To measure the proportion of subjects requiring an intensification of anti-diabetic regimen versus placebo over time
- To measure the proportion of subjects requiring a relaxation of their anti-diabetic regimen versus placebo over time
- To measure the incidence of hospitalization for heart failure among all subjects and among subjects with a history of heart failure at baseline

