8. EFFICACY

Efficacy data include HbA_{1c}, FPG, body weight, and blood pressure. All changes from baseline will be calculated as the post-treatment value minus the baseline value. All continuous efficacy data will be summarized for observed and change values by treatment and visit. The proportion of subjects requiring an intensification of anti-diabetic regimen, proportion of subjects requiring a relaxation of anti-diabetic regimen, incidence of and time to hospitalization for heart failure will be summarized by frequency, and the proportion by treatment and visit.

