8.2.2.6. Time to first use of intensification or relaxation of hypoglycemic agent

Kaplan-Meier plots will be prepared for these endpoints by treatment. These endpoints will be analyzed using Cox proportional hazards models with treatment, region, baseline eGFR categories (<60 or ≥60 mL min⁻¹ per 1.73 m²), baseline BMI (< or ≥25 kg m⁻²), history of heart failure (yes or no), insulin use or not, and baseline HbA_{1c} as the covariates. Maximum likelihood with ties method of Breslow will be used. The hazard ratio of the endpoint, p-value with its two-sided 95% CIs presented. Subjects who withdraw from the trial and have post-baseline assessments will be censored at the last contact date. Subjects who have no follow-up event data will be censored at the date of randomization + 1 day. Analysis will also be conducted for subjects who have been prescribed insulin or sulfonylurea to control their diabetes. Time to first intensification of hypoglycemic agent will also be conducted for subjects who have been prescribed insulin or sulfonylurea to control their diabetes.

8.2.2.7. Time to hospitalization for heart failure and time to cardiovascular death or hospitalization for a heart failure event in all subjects and in subjects with a history of heart failure

Same analyses in Section 8.2.2.6 will be conducted. History of heart failure will not be used in the analysis model in subjects with a history of heart failure.

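### For intensification and relaxation of anti-diabetic therapy, SAP 8.2.2.4 drops the protocol's by-visit GEE odds ratios for a single logistic model with no time horizon, and SAP 12 does not declare the change

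*Combined protocol and SAP*

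**What the plan says.** The objective in protocol 2.2 is "To measure the proportion of subjects requiring an intensification of anti-diabetic regimen versus placebo over time". Relaxation has a parallel objective, and SAP 3.2 keeps both.

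For the method, protocol 9.6.2 states: "Endpoints measuring proportions over time will be analyzed using generalized estimating equation (GEE) logistic regression". The output is by visit: "odds ratios will be estimated from the model with the corresponding p-values and their two-sided 95% CIs presented at each visit".

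SAP 8.2.2.4, which covers the proportions with intensification and relaxation, states: "These endpoints will be analyzed using logistic regression". The listed terms are treatment, region, baseline eGFR category, baseline BMI category, heart-failure history, insulin use and baseline HbA1c. There is no visit term, fixed time point or adjustment for length of follow-up.

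Three other parts of the SAP bear on this:

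- Section 8 keeps a description over time. These proportions "will be summarized by frequency, and the proportion by treatment and visit".
- Section 8.2.2.6 plans Kaplan-Meier plots and a time-to-first-event model: "These endpoints will be analyzed using Cox proportional hazards models with treatment, region, baseline eGFR categories" and further baseline terms.
- Section 6.2.7 does not count an increase in therapy after the last day of study drug as intensification.

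SAP 12 lists the changes from the protocol: full analysis set to ITT, the covariates, the imputation for the primary endpoint, and added exploratory items. The SAP revision history does not mention the move away from GEE either.

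**The concern.** The SAP keeps an objective worded over time but removes the only between-arm comparison that the protocol set at individual visits. The continuous over-time endpoints (HbA1c, FPG, weight, SBP) keep models with visit and treatment-by-visit terms in SAP 8.2.2.2 and 8.2.2.3; these two proportions do not.

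With no horizon stated, the natural reading is that each subject is classed as ever or never intensified over the whole study. Subjects are observed for different lengths of time, and intensification can count only while the subject is on study drug. The odds ratio then reflects the treatment effect together with time on drug in each arm. If one arm stops drug faster, it has less opportunity to record an intensification, and the odds ratio moves away from 1 with no treatment effect present. Because the change is undeclared, a reader comparing the report with the protocol would not know that the by-visit comparison had been planned and dropped.

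**Working it through.** **Text.** The item list in protocol 9.6.2 is uneven: the intensification item lacks the words about time, while the relaxation item has them. The objectives in protocol 2.2 and the synopsis endpoints carry the wording for both, so both belong to the GEE class. SAP 8.2.2.4 has no counterpart to the visit dimension, and SAP 12 does not mention it.

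**Inputs from the documents.** Planned follow-up is 1 to 3 years (protocol 9.2). Treatment duration is expected to average 2 to 3 years (protocol 3.3.4). Annual premature withdrawal is 6.5%, not split by arm (protocol 9.2). Intensification is not counted after the last dose (SAP 6.2.7). The plan gives no intensification rate and no drug-stopping rate by arm, so there is no plan figure to reproduce here.

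**Assumptions.** Intensification hazard h = 0.25 a year in both arms (no effect). Drug-stopping hazard s = 0.067 a year on bexagliflozin, borrowed from the withdrawal rate (−ln(1 − 0.065) = 0.067), and twice that, 0.134, on placebo. GEE status at a visit is taken as cumulative.

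**Formula.** The probability of a counted intensification by time u is

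p(u) = h/(h + s) × (1 − e^(−(h + s)u)).

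With follow-up uniform on (a, b), its mean is

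h/(h + s) × [1 − (e^(−(h + s)a) − e^(−(h + s)b)) / ((h + s)(b − a))].

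**Whole study, 1 to 3 years.**
- Bexagliflozin: 0.25/0.317 × [1 − (0.7283 − 0.3864)/0.634] = 0.363.
- Placebo: 0.25/0.384 × [1 − (0.6811 − 0.3160)/0.768] = 0.342.
- Odds ratio: (0.3633/0.6367)/(0.3415/0.6585) = 1.10.

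**All horizons, no true effect.**

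| Horizon | Bexagliflozin | Placebo | Odds ratio |
|---|---|---|---|
| Week 24 (0.46 yr) | 0.107 | 0.105 | 1.02 |
| Week 48 (0.92 yr) | 0.199 | 0.194 | 1.04 |
| Week 96 (1.84 yr) | 0.349 | 0.330 | 1.09 |
| Week 144 (2.76 yr) | 0.460 | 0.425 | 1.15 |
| Whole study, 1–3 yr | 0.363 | 0.342 | 1.10 |
| Whole study, 2–3 yr | 0.430 | 0.400 | 1.13 |

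With equal stopping the two probabilities are identical and the odds ratio is exactly 1.00. With the stopping rates reversed, the 1 to 3 year value is 1/1.10 = 0.91. Over h from 0.15 to 0.35 and stopping of 0.067 against 0.134 or 0.10 against 0.20, the null odds ratio runs from 1.09 to 1.16 (1–3 years) and from 1.11 to 1.22 (2–3 years).

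**Dependence on the horizon without unequal stopping.** At a constant hazard ratio of 0.7 and an assumed 40% two-year placebo risk, the ever/never odds ratio is 0.673, 0.645 and 0.616 at 1, 2 and 3 years. This is the usual gap between an odds ratio and a hazard ratio, not bias, but it means the number has no fixed meaning until a horizon is given.

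**Cox.** SAP 8.2.2.6 censors subjects who withdraw from the trial at last contact. It states no censoring at last dose for subjects who stop drug and stay in the study. A simulation under the same null assumptions (150,000 subjects, 2:1) gave a hazard ratio of about 1.07 (1–3 years) to 1.09 (2–3 years) when such subjects stay at risk, and 1.00 when they are censored at last dose.

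**The case against.** Much of the defence stands. Section 8 of the SAP still tabulates the proportions by arm and visit, and Kaplan-Meier plots show them over time, so an objective to measure proportions is largely met descriptively. Cox models handle unequal follow-up. Protocol 9.1 says that the separate analysis plan becomes the final one, so the SAP may refine an exploratory model; only the entry in section 12 is missing. SAP 8.2.2 treats these endpoints as exploratory, with nominal p-values and no multiplicity adjustment.

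Three stronger readings are tempting and are not supported.

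- **That heart-failure hospitalization is affected too.** SAP 8.2.2.5 also uses logistic regression, but the objective reads "To measure the incidence of hospitalization for heart failure among all subjects and among subjects with a history of heart failure at baseline". That is an incidence with no wording about time, so its assignment to GEE would be an inference. No on-drug limit is stated for it, and protocol 6.10.12 has hospitalization for heart failure adjudicated and follows subjects for cardiovascular events after study drug is withdrawn. For the time-to-event version, SAP 8.2.2.7 says: "Same analyses in Section 8.2.2.6 will be conducted". At the plan's own rates (1250 × 0.017 + 400 × 0.102 = 62.05, matching its 62, or 3.8% over two years) the odds ratio for a hazard ratio of 0.7 moves only from 0.698 to 0.694 between 1 and 3 years.
- **That the planned comparison is biased.** It is biased only if time on drug differs by arm, and the documents give no stopping rates by arm.
- **That restoring GEE at every visit removes the problem.** It does not: the illustration gives 1.15 at week 144. The distortion comes from the last-dose counting rule combined with unequal stopping, not from logistic regression as against GEE.

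**Conclusion.** The point holds for intensification and relaxation only. The SAP drops a prespecified by-visit inferential comparison, leaves the horizon of its replacement unstated, and does not declare the change. What is lost is the by-visit odds ratio with its confidence interval and p-value, not the by-visit proportions.

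The dependence on time on drug is firm for intensification because of the last-dose rule in SAP 6.2.7. For relaxation, SAP 6.2.8 refers to the treatment period without that explicit cut-off, so the argument there is weaker. Under the assumed rates, a null effect would read as an odds ratio of about 1.10 to 1.13 over the whole study, against 1.02 to 1.04 at weeks 24 and 48. These sizes rest on the assumed hazard, on assumed unequal stopping and on the ever/never reading of SAP 8.2.2.4. Severity is low: no confirmatory claim depends on these endpoints, and a Cox analysis is already planned.

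**What to change.** In SAP 8.2.2.4, estimate the intensification and relaxation odds ratios at weeks 24 and 48, either by logistic regression at each time point or by GEE over visits up to week 48. Both fall inside the 52-week minimum and before most of the drug stopping that drives the distortion.

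In SAP 8.2.2.6, make Cox the whole-study analysis and censor intensification at the last dose, so that time at risk matches the counting rule in 6.2.7. Record the move from all-visit GEE in SAP 12.

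The cost is some SAP wording and a few more model runs on data already collected. The downside is that events after week 48 enter only the Cox analysis. SAP 8.2.2.5 on heart-failure hospitalization needs no change on this account.
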